13.0 STUDY MANAGEMENT

13.1 CONFLICT OF INTEREST

Any investigator who has a conflict of interest with this study (patent ownership, royalties, or financial gain greater than the minimum allowable by their institution, etc.) must have the conflict reviewed by the UTSW COI Committee and IRB according to UTSW Policy on Conflicts of Interest. All investigators will follow the University conflict of interest policy.

13.2 INSTITUTIONAL REVIEW BOARD (IRB) APPROVAL AND CONSENT

It is expected that the IRB will have the proper representation and function in accordance with federally mandated regulations. The IRB must approve the consent form and protocol.

In obtaining and documenting informed consent, the investigator should comply with the applicable regulatory requirement(s), and should adhere to Good Clinical Practice (GCP) and to ethical principles that have their origin in the Declaration of Helsinki.

Before recruitment and enrollment onto this study, the subject will be given a full explanation of the study and will be given the opportunity to review the consent form. Each consent form must include all the relevant elements currently required by the FDA Regulations and local or state regulations. Once this essential information has been provided to the subject and the investigator is assured that the subject understands the implications of participating in the study, the subject will be asked to give consent to participate in the study by signing an IRB-approved consent form.

Prior to a patient's participation in the trial, the written informed consent form should be signed and personally dated by the subject and by the person who conducted the informed consent discussion.

14.0 RECRUITMENT AND REGISTRATION PROCEDURES

14.1 RECRUITMENT PLAN

The study will be open to all patients seen at the UT Southwestern Medical Center (including Parkland Health & Hospital System, University Hospital-Clements and

Zale, and the Harold C. Simmons Cancer Center) who meet the eligibility criteria outlined in Section 5.0.

In addition, a description of the study and the enrollment criteria will be placed on the UT Southwestern Medical Center website to maximize patient recruitment. Patients will be identified from surgical, hepatology, gastroenterology, radiology and medical oncology clinics for treatment of their disease. After a discussion of the patient's disease and a formulation of the initial treatment plan, the physician-investigator will describe the study to the patient. The protocol will be discussed in a private clinic room or office. Details including the risks and obligations of the subjects will be explained. For non-English speaking patients, an independent translator will be available to communicate the details of the protocol. A research coordinator will be available either in the clinic or by phone to answer any additional questions.

Upon completion of the informed consent form and confirmation of protocol eligibility, the Clinical Research Office (CRO) at the Harold C. Simmons Cancer Center will be notified of the new enrollment. All patients will be entered into the Velos Clinical Trials Management System for ongoing monitoring. All data collected will be entered into the password protected REDCap electronic data capture system.

The investigators take due notice of the NIH policy concerning inclusion of women and minorities in clinical research populations. There will be no limitation to access with regard to race or gender. Patients will be required to read, agree to and sign an IRB-approved informed consent form prior to registration on this trial. The registration procedure will be conducted as described above. Patients will not receive payment for their participation on this study.

14.2 STUDY SUBJECT IDENTIFICATION NUMBER

All subjects will be assigned a study number that is not linked to their personal identifiers to prevent loss of confidentiality. The number will be the Site Number, 01, 02, etc. followed by a sequential number starting with number 001. For example, the first subject enrolled from site # 01 will be assigned study subject number 01-001; the next will be 01-002, and so forth. For this protocol, current sites are: 01 – UTSW and 02 – PHHS. Any additional sites added to this protocol will be numbered sequentially...03, 04, etc. This number will be assigned by the UTSW - Clinical Research Manager or QA Coordinator or delegate upon confirmation of subject eligibility during the subject registration process.

14.3 SUBJECT REGISTRATION

Following completion of baseline assessments and confirmation of subject eligibility, patients will be assigned a subject identification number by the UTSW - CRM or delegate and registered into Velos, the UTSW Clinical Trial Management System (CTMS). Subject registration will be confirmed (within

24 hours) once the following documents have been received by the UTSW-CRM or delegate.

- Signed copy of the Informed Consent signature page;
- Inclusion/Exclusion worksheet signed by the coordinator and treating physician;

All subjects must be registered with the UTSW - CRM before enrollment to study. To register a subject, email the above supporting documents to the UTSW – QA Coordinators [contact] or call [contact], Monday through Friday, 8:00a.m. - 4:00p.m. CST.

15.0 PROTECTION OF HUMAN SUBJECTS

Participation in this trial is voluntary. All patients will be required to sign a statement of informed consent, which must conform to IRB guidelines.

Inclusion of Women and Minorities: Patients of all races, both male and female, will be accepted into the protocol.

Exclusion of Lactating or Pregnant Women: Children have been excluded from this study. Hepatocellular carcinoma is an adult cancer. Thus, the relevance of this drug to the pediatric population has not been established. Lactating and pregnant women are also excluded because of potential anti-proliferative effects of therapy that may be harmful to the developing fetus or nursing infant.

Benefits: It is possible that this treatment will result in shrinkage of hepatocellular carcinoma or in a stabilization of an otherwise progressing disease. It is not known, of course, whether these or any other favorable events will occur. It is not known whether this treatment will affect overall survival of the patients.

Costs: The patient will be responsible for the costs of standard medical care, including, all hospitalizations, even for complications of treatment. LEE011 will be supplied to patients without costs from Novartis Pharmaceuticals. Patients will not be responsible for the costs of tissue or serum procurement (including image guided biopsies) obtained for research purposes.

Incentives: No incentives will be offered to patients/subjects for participation in this study.

Alternatives: For patients with advanced hepatocellular carcinoma, alternative treatments may include other chemotherapy regimens or loco-regional therapies including transarterial chemoembolization and radiofrequency ablation. At present, no specific treatment approach is considered standard of care for the disease. Patients may be eligible for other investigational studies.

Confidentiality: Every effort will be made to maintain patient confidentiality. Research and hospital records are confidential. Patient's name or any personally identifying information will not be used in reports or publications resulting from this study. The Food and Drug Administration or other authorized agencies (i.e., qualified monitors from UT Southwestern Medical Center, the NCI, etc.), may review patients records and pathology slides, as required.

16.0 DATA AND SAFETY MONITORING PLAN

Trial monitoring will be conducted no less than annually and refers to a regular interval review of trial related activity and documentation performed by the DOT, which includes but is not limited to accuracy of case report forms, protocol compliance, timeliness and accuracy of Velos entries and AE/SAE management and reporting. Documentation of trial monitoring will be maintained along with other protocol related documents and will be reviewed during internal audit.

Study PI or designated Co-investigator and the research coordinator will attend the weekly Phase I research meeting during the dose escalation phase. Toxicity and dose escalation reviews will be performed in real-time by the Phase I DOT and DSMC. As the study transitions to the Phase II stage, toxicity will be reviewed at the GI DOT research meetings and by DSMC. These reviews will be documented by distributing reports of the findings to the members of the GI DOT and investigators.

The UTSW Simmons Cancer Center (SCC) Data Safety Monitoring Committee (DSMC) is responsible for monitoring data quality and patient safety for all UTSW SCC clinical trials. As part of that responsibility, the DSMC reviews all local serious adverse events and unanticipated problems in real time as they are reported and reviews adverse events on a quarterly basis. The quality assurance activity for the Clinical Research Office provides for periodic auditing of clinical research documents to ensure data integrity and regulatory compliance. A copy of the DSMC plan is available upon request.

The SCC DSMC meets quarterly and conducts annual comprehensive reviews of ongoing clinical trials, for which it serves as the DSMC of record. The QAC works as part of the DSMC to conduct regular audits based on the level of risk. Audit findings are reviewed at the next available DSMC meeting. In this way, frequency of DSMC monitoring is dependent upon the level of risk. Risk level is determined by the DSMC Chairman and a number of factors such as the phase of the study; the type of investigational agent, device or intervention being studied; and monitoring required to ensure the safety of study subjects based on the associated risks of the study. Protocol-specific DSMC plans must be consistent with these principles. Safety is monitored in real-time as serious adverse events and adverse events, which are unanticipated problems, are submitted to the DSMC and IRB with attributions.

17.0 ADHERENCE TO THE PROTOCOL

Except for an emergency situation in which proper care for the protection, safety, and well-being of the study subject requires alternative treatment, the study shall be conducted exactly as described in the approved protocol.

17.1 EMERGENCY MODIFICATIONS

Investigators may implement a deviation from, or a change of, the protocol to eliminate an immediate hazard(s) to trial subjects without prior IRB approval.

For any such emergency modification implemented, an IRB modification form must be completed within five (5) business days of making the change.

17.2 OTHER PROTOCOL DEVIATIONS/VIOLATIONS

All other planned deviations from the protocol must have prior approval by the Principal Investigator and the IRB. According to the IRB, a protocol deviation is any unplanned variance from an IRB approved protocol that:

- Is generally noted or recognized after it occurs
- Has no substantive effect on the risks to research participants
- Has no substantive effect on the scientific integrity of the research plan or the value of the data collected
- Did not result from willful or knowing misconduct on the part of the investigator(s).

An unplanned protocol variance is considered a violation if the variance:

- Has harmed or increased the risk of harm to one or more research participants.
- Has damaged the scientific integrity of the data collected for the study.
- Results from willful or knowing misconduct on the part of the investigator(s).
- Demonstrates serious or continuing noncompliance with federal regulations, State laws, or University policies.

If a deviation or violation occurs without prior approval from the Principal Investigator, please follow the guidelines below:

If {non-Research Office} managed study, please maintain the following language in your protocol:

Protocol Deviations: Personnel will report to any sponsor or data and safety monitoring committee in accordance with their policies. Deviations should be summarized and reported to the IRB at the time of continuing review.

Protocol Violations: Study personnel should report violations within two (2) week of the investigator becoming aware of the event using the same IRB online mechanism used to report Unanticipated Problems.

17.3 AMENDMENTS TO THE PROTOCOL

Should amendments to the protocol be required, the amendments will be originated and documented by the Principal Investigator. A summary of changes document outlining proposed changes as well as rationale for changes, when appropriate, is highly recommended. When an amendment to the protocol substantially alters the study design or the potential risk to the patient, a revised consent form might be required.

The written amendment, and if required the amended consent form, must be sent to the IRB for approval prior to implementation.

17.4 RECORD RETENTION

Study documentation includes all Case Report Forms, data correction forms or queries, source documents, Sponsor-Investigator correspondence, monitoring logs/letters, and regulatory documents (e.g., protocol and amendments, IRB correspondence and approval, signed patient consent forms).

Source documents include all recordings of observations or notations of clinical activities and all reports and records necessary for the evaluation and reconstruction of the clinical research study.

Government agency regulations and directives require that the study investigator retain all study documentation pertaining to the conduct of a clinical trial. In the case of a study with a drug seeking regulatory approval and marketing, these documents shall be retained for at least two years after the last approval of marketing application in an International Conference on Harmonization (ICH) region. In all other cases, study documents should be kept on file until three years after the completion and final study report of this investigational study.

17.5 OBLIGATIONS OF INVESTIGATORS

The Principal Investigator is responsible for the conduct of the clinical trial at the site in accordance with Title 21 of the Code of Federal Regulations and/or the Declaration of Helsinki. The Principal Investigator is responsible for personally overseeing the treatment of all study patients. The Principal Investigator must assure that all study site personnel, including sub-investigators and other study staff members, adhere to the study protocol and all FDA/GCP/NCI regulations and guidelines regarding clinical trials both during and after study completion.

The Principal Investigator at each institution or site will be responsible for assuring that all the required data will be collected and entered onto the Case Report Forms. Periodically, monitoring visits may be conducted and the Principal Investigator will provide access to his/her original records to permit verification of proper entry of data. At the completion of the study, all case report forms will be reviewed by the

Principal Investigator and will require his/her final signature to verify the accuracy of the data.

19.0 APPENDICES

In general, the use of any concomitant medication deemed necessary for the care of the patient is permitted in this study, except as specifically prohibited below. Combination administration of study drugs could result in drug-drug interactions (DDI) that could potentially lead to reduced activity or enhanced toxicity of the concomitant medication and/or LEE011.

The following lists are not comprehensive and are only meant to be used as a guide. The lists are based on the Oncology Clinical Pharmacology Drug-Drug Interaction Database (release date: 29 Oct 2012), which was compiled from the Indiana University School of Medicine's P450 Drug Interaction Table (<http://medicine.iupui.edu/clinpharm/ddis/main-table/>) and supplemented with the FDA Draft Guidance for Industry, Drug Interaction Studies – Study Design, Data Analysis, and Implications for Dosing and Labeling (February 2012) (<http://www.fda.gov/downloads/drugs/guidancecomplianceregulatoryinformation/guidances/ucm292362.pdf>), and the University of Washington's Drug Interaction Database (<http://www.druginteractioninfo.org/>). For current lists of medications that may cause QT prolongation and/or torsades de pointes (TdP), refer to the CredibleMeds® website (<https://crediblemeds.org/>). Please contact the medical monitor with any questions.

Appendix Table 1: List of medications to be used with caution during study drug treatment

Category	Drug Name
Moderate CYP3A4/5 inhibitors	Amprenavir, aprepitant, atazanavir, casopitant, cimetidine, ciprofloxacin, darunavir, diltiazem, dronedarone, fluconazole, fosamprenavir, grapefruit juice (citrus paradisi fruit juice), imatinib, Schisandra sphenanthera ¹ , tofisopam, verapamil
Moderate CYP3A4/5 inducers	Bosentan, efavirenz, etravirine, genistein, modafinil, nafcillin, talviraline, thioridazine
Sensitive CYP3A4/5 substrates ¹	Alpha-dihydroergocryptine, aplaviroc, aprepitant, atorvastatin, brecanavir, brotizolam, budesonide, buspirone, capravirine, casopitant, darifenacin, darunavir, dasatinib, dronedarone, ebastine, eletriptan, eplerenone, everolimus, felodipine, fluticasone, lovastatin, lumefantrine, lurasidone, maraviroc, midazolam, neratinib, nisoldipine, perospirone, quetiapine, ridaforolimus, sildenafil, simvastatin, ticagrelor, tolvaptan, triazolam, vardenafil, vicriviroc
Strong BSEP inhibitors	Bosentan, fusidate, glibenclamide, lovastatin, sulindac, troglitazone (TGZ-sulfate)
Medications that carry a possible risk for QT prolongation ²	Alfuzosin, amantadine, atazanavir, chloral hydrate, clozapine, dolasetron, dronedarone, eribulin, escitalopram, famotidine, felbamate, fingolimod, foscarnet, fosphenytoin, gatifloxacin, gemifloxacin, granisertron, iloperidone, indapamide, isradipine, lapatinib, levofloxacin, lithium, moexipril, nicardipine, nilotinib, octreotide, ofloxacin, ondansetron, oxytocin, paliperidone, pasireotide, quetiapine, ranolazine, risperidone, roxithromycin, sertindole, sunitinib, tamoxifen, tizanidine, vardenafil, venlafaxine, ziprasidone
MATE1 and OCT2 substrates ³	Acyclovir, amantadine, amiloride, cephalexin, cephradine, cimetidine, famotidine, fexofenadine, memantine, metformin (also a substrate for OCT1, MATE1, and MATE2K), pindolol, procainamide, ranitidine, and varencicline
BCRP substrates	Daunorubicin, doxorubicin, rosuvastatin, sulfasalazine, topotecan

¹ Sensitive substrates: Drugs whose plasma AUC values have been shown to increase 5-fold or higher when co-administered with a potent inhibitor.
 
² Source: www.crediblemeds.org
 
³ Source: FDA Draft Guidance for Industry, Drug Interaction Studies – Study Design, Data Analysis, and implications for Dosing and Labeling (February 2012) and Yonezawa and Inui (2011) Importance of the multidrug and toxin extrusion MATE/SLC47A family to pharmacokinetics, pharmacodynamics/toxicodynamics and pharmacogenomics. Br J Pharmacology 164:1817-25
	

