5.2 EXCLUSION CRITERIA

5.2.1 Patient who received any CDK4/6 inhibitor;

5.2.2 Patient who has received previous systemic therapy or TACE for HCC;

5.2.3 Clinically significant, uncontrolled heart disease and/or recent events including any of the following:

5.2.3.1 History of acute coronary syndromes (including myocardial infarction, unstable angina, coronary artery bypass grafting,

- 5.2.3.2 coronary angioplasty, or stenting) or symptomatic pericarditis within 12 months prior to screening;
- 5.2.3.3 History of documented congestive heart failure (New York Heart Association functional classification III-IV);
- 5.2.3.4 Documented cardiomyopathy;
- 5.2.3.5 Patient has a left ventricular ejection fraction <50% as determined by MUGA scan or ECHO at screening;
- 5.2.3.6 History of any cardiac arrhythmias, e.g., ventricular, supraventricular, nodal arrhythmias, or conduction abnormality within 12 months of screening;
- 5.2.3.7 Bradycardia (heart rate <50 at rest), by ECG or pulse, at screening;
- 5.2.3.8 Congenital long QT syndrome or family history of long QT syndrome;
- 5.2.3.9 Systolic Blood Pressure (SBP) >160 or <90 mm Hg;
- 5.2.4 On screening inability to determine the QTcF interval on the ECG (i.e.: Unreadable or Not Interpretable) or QTcF > 450 msec (using Fridericia's correction). All as determined by screening ECG (mean of triplicate ECGs);
- 5.2.5 Patient is currently receiving any of the following medications and cannot be discontinued 7 days prior to treatment (see appendix 1 for details):
 - 5.2.5.1 Known strong inducers or inhibitors of CYP3A4/5 or bile salt pump efflux, including grapefruit, grapefruit hybrids, pummelos, star-fruit, and Seville oranges;
 - 5.2.5.2 That have a known risk to prolong the QT interval or induce Torsades de Pointes;
 - 5.2.5.3 Herbal preparations/medications, dietary supplements;
 - 5.2.5.4 That have a narrow therapeutic window and are predominantly metabolized through CYP3A4/5;
- 5.2.6 Tumor involvement > 50% of the liver;
- 5.2.7 Patient has a known history of HIV infection (testing is not required);
- 5.2.8 Patient has any other concurrent severe and/or uncontrolled medical condition that would, in the investigator's judgment, cause unacceptable safety risks, contraindicate patient participation in the study or compromise

compliance with the protocol (e.g. chronic pancreatitis, active untreated or uncontrolled fungal, bacterial, or viral infections, etc.);

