6.4 LEE011 DOSING

LEE011 must be taken as follows:

- Patients should be instructed to take the LEE011 capsules with a large glass of water (~250 mL or 8 oz.) at the same time each day;
- LEE011 can be taken without regard to meals; however dietary habits around the time of dosing should be as consistent as possible throughout the study;
- Patients should be instructed to swallow the LEE011 capsules whole and not to chew, crush or open them;
- If vomiting occurs during the course of treatment, no re-dosing of the patient is allowed before the next scheduled dose;
- Any doses that are missed (not taken within 6 hours of the intended time) should be skipped and should not be replaced or made up on a subsequent day;
- Patients must avoid consumption of grapefruit, Seville oranges or products containing the juice of each during the entire study and preferably 7 days before the first dose of study medication, due to potential CYP3A4 interaction with the study medications. Orange juice is allowed.

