Appendix Table 2: List of prohibited medications during study drug treatment

Category	Drug Name
Strong CYP3A4/5 inhibitors	Boceprevir, clarithromycin, cobicistat, conivaptan, elvitegravir, indinavir, itraconazole, ketoconazole, lopinavir, mibefradil, nefazodone, nelfinavir, posaconazole, ritonavir, saquinavir, telaprevir, telithromycin, tipranavir, troleandomycin, voriconazole
Strong CYP3A4/5 inducers	Avasimibe ^{2,3} , carbamazepine, mitotane, phenobarbital, phenytoin, rifabutin, rifampin (rifampicin) ³ , St. John's wort (hypericum perforatum) ³
CYP3A4/5 substrates with NTI ¹	Alfentanil, astemizole, cisapride, cyclosporine, diergotamine (dihydroergotamine), ergotamine, fentanyl, pimozone, quinidine, sirolimus, tacrolimus, terfenadine
Medications with a known risk for QT prolongation ⁴	Amiodarone, arsenic trioxide, astemizole, azithromycin, bepridil, chloroquine, chlorpromazine, cisapride, citalopram, clarithromycin, disopyramide, dofetilide, domperidone, droperidol, erythromycin, flecainide, halofantrine, haloperidol, ibutilide, levomethadyl, mesoridazine, methadone, moxifloxacin, pentamidine, pimozone, probucol, procainamide, quinidine, sotalol, sparfloxacin, terfenadine, thioridazine, vavdetanib
Herbal preparations/medications	Herbal preparations/medications are prohibited throughout the study. These herbal medications include, but are not limited to: St. John's wort, Kava, ephedra (ma huang), ginkgo biloba, dehydroepiandrosterone (DHEA), yohimbe, saw palmetto, and ginseng. Patients should stop using these herbal medications 7 days prior to first dose of study drug.
Other investigational and antineoplastic therapies	Other investigational therapies must not be used while the patient is on the study. Anticancer therapy (chemotherapy, biologic or radiation therapy, and surgery) other than the study treatments must not be given to patients while the patient is on the study medication. If such agents are required for a patient then the patient must be discontinued study drug.

¹ NTI = narrow therapeutic index drugs whose exposure-response indicates that increases in their exposure levels by the concomitant use of potent inhibitors may lead to serious safety concerns (e.g., Torsades de Pointes).
 
² Herbal product
 
³ P-gp inducer
 
⁴ Source: www.crediblemeds.org
	

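### Appendix Table 1 lists as use-with-caution four items that the protocol prohibits elsewhere, and 6.12.3 names fentanyl, which Appendix Table 2 prohibits

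*Combined protocol and SAP*

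**What the plan says.** Appendix Table 1 is the use-with-caution list. Its moderate CYP3A4/5 inhibitor row contains "grapefruit juice (citrus paradisi fruit juice), imatinib, Schisandra sphenanthera". Its moderate inducer row reads "Bosentan, efavirenz, etravirine, genistein, modafinil, nafcillin, talviraline, thioridazine", and its MATE1/OCT2 substrate row ends "pindolol, procainamide, ranitidine, and varencicline".

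Other parts of the same document prohibit these items:

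- **Grapefruit.** Section 6.4: "Patients must avoid consumption of grapefruit, Seville oranges or products containing the juice of each during the entire study". Exclusion 5.2.5.1 groups it with strong agents: "Known strong inducers or inhibitors of CYP3A4/5 or bile salt pump efflux, including grapefruit, grapefruit hybrids, pummelos, star-fruit, and Seville oranges". Appendix Table 2, the prohibited list, does not mention it.
- **Thioridazine and procainamide.** The known-QT-risk row of Appendix Table 2 includes "procainamide, quinidine, sotalol, sparfloxacin, terfenadine, thioridazine".
- **Herbals.** Section 6.9 and Appendix Table 2 prohibit them as a class.

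Three passages bear on how the lists are used. The opening of Section 19.0 allows any medication needed for care unless it is prohibited in what follows, describes the lists as a guide, and refers questions to the medical monitor. Section 6.9 asks sites to avoid caution items where possible, but lets them be given with care when unavoidable. Exclusion 5.2.5 covers patients whose listed medication "cannot be discontinued 7 days prior to treatment (see appendix 1 for details").

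Section 6.12.3 names fentanyl for sedation before chemoembolization. Appendix Table 2 lists fentanyl among the prohibited narrow-therapeutic-index CYP3A4/5 substrates.

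**The concern.** A coordinator who looks up a drug, finds it in Appendix Table 1 and stops there would treat it as conditionally allowed. Thioridazine appears as an enzyme inducer and procainamide as a transporter substrate, so neither row hints at the QT prohibition one table later. Grapefruit juice appears as a moderate inhibitor, and checking Appendix Table 2 would not correct the impression.

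What is at stake is avoidable exposure. Section 1.7.1 says that CYP3A4 inhibitors or inducers may affect LEE011 elimination. Section 1.7.3 reports QT prolongation in the dog telemetry study, and Table 2-2 reports it in 10 of 67 patients at 600 mg (15%), none at grade 3 or 4. Those figures show why QT co-medication matters here. They describe LEE011 itself and do not measure the effect of the list error.

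The fentanyl conflict differs in kind: it arises from following the protocol's own procedure, not from misreading a list.

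**Working it through.** The plan states no figure to reproduce. The check sets the lists side by side and counts the overlap.

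**Name overlap.** Each drug name was taken once, even when it appears in several rows. Appendix Table 1 has 116 distinct names and Appendix Table 2 has 67. Names in both: 2 (thioridazine, procainamide), and 2/116 = 1.7%. Adding grapefruit juice and Schisandra gives 2 + 1 + 1 = 4 items, and 4/116 = 3.4%.

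| Item | Row in Appendix Table 1 | Where prohibited | Covered by the opening of Section 19.0? |
|---|---|---|---|
| Thioridazine | Moderate CYP3A4/5 inducer | Appendix Table 2, by name, known QT risk | Yes |
| Procainamide | MATE1/OCT2 substrate | Appendix Table 2, by name, known QT risk | Yes |
| Schisandra | Moderate CYP3A4/5 inhibitor | 6.9 and Appendix Table 2, as a herbal | Yes, through the class |
| Grapefruit juice | Moderate CYP3A4/5 inhibitor | 6.4; 5.2.5.1 before treatment | No, absent from Appendix Table 2 |

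**Cross-references.** Exclusion 5.2.5 deals with strong CYP3A4/5 agents, known-QT drugs, herbals and narrow-window substrates. These are mostly Appendix Table 2 categories, but the pointer given matches, by number, the caution table. The caution paragraph in 6.9 first cites Table 2, which by number suggests the prohibited list, and only later cites Appendix Table 1.

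**Fentanyl exposure.**

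1. Sections 6.12.7 and 7.3.1 allow up to 4 chemoembolizations in the first 6 months. LEE011 starts at least 7 days after the first, so up to 4 − 1 = 3 repeat procedures per patient can follow the start of LEE011 in that period. Further procedures are allowed later if indicated.
2. Table 7.1 marks chemoembolization at Day 1 visits, directly after the Days 22–28 rest.
3. With the mean effective half-life of 32.6 hours in Section 1.7.4.1, seven days is 7 × 24 / 32.6 = 168 / 32.6 = 5.15 half-lives, and 0.5^5.15 ≈ 0.03. About 3% of the drug would remain. This assumes first-order elimination and carries over a half-life from the first-in-human study, not from patients with HCC.
4. Footnote 13 to Table 7.1 lets the post-procedure visit serve as Day 1, which would also put the procedure before LEE011 restarts.
5. However, Table 7.1 marks LEE011 at the same Day 1 visits, and neither 6.12.3 nor 6.12.7 states a hold or an exception.

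The schedule therefore probably limits co-exposure, but the text does not guarantee it.

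**The case against.** The strongest reply is that the protocol already settles most of this. Section 19.0 makes specific prohibition the exception to a general permission. Section 6.9 sets out the prohibited classes immediately after the caution paragraph. Exclusions 5.2.5.2 and 5.2.5.3 keep out patients who cannot stop known-QT drugs or herbals. Section 19.0 also sends sites to a maintained QT list and to the medical monitor. For grapefruit, a mandatory dosing instruction in 6.4 outranks a list offered only as a guide. Scheduled ECGs and the QTc rules add a backstop.

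Most of that stands, and it rules out several stronger readings:

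- **That nothing decides which status governs.** The opening of Section 19.0 implies that prohibition prevails for anything named or classed in Appendix Table 2. What is missing is an explicit sentence for a drug on both lists, and any cover there for grapefruit juice.
- **That the anticancer drugs in Appendix Table 1 are further contradictions.** The BCRP row, for example, reads "Daunorubicin, doxorubicin, rosuvastatin, sulfasalazine, topotecan". The class ban in 6.9 and Appendix Table 2 sits above that list, and Appendix Table 2 requires LEE011 to stop if such an agent is needed. Doxorubicin is part of the study chemoembolization. The documents do not label the individual drugs by class, so any count rests on outside knowledge.
- **That the dose-limiting toxicity count is distorted.** Table 6.2 requires at least possible attribution to LEE011, and the QTc rules call for a concomitant-medication review. The documents give no rate of use from which to estimate an effect.

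The reply does not remove the double listings. The conditional permission in 6.9 applies to an item as soon as it is found in Appendix Table 1. ECGs act after exposure, and the medical monitor helps only a reader who notices the conflict. Nothing in the reply supplies the missing fentanyl exception.

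**Conclusion.** The point holds as a minor patient-safety correction. Two drugs are on both lists by name. Grapefruit juice is a caution item against an explicit ban, and one herbal is a caution item against a class ban. Fentanyl is named in the procedure text and prohibited during study drug treatment.

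The conclusion rests on the drug names as they stand in the two tables and, for Schisandra only, on general knowledge that it is a herbal. The documents give no frequency of use for any of these items, so the number of patients affected cannot be stated. Nothing here bears on sample size, error rates or endpoints.

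**What to change.** - Delete thioridazine, procainamide, grapefruit juice and Schisandra from Appendix Table 1, and add grapefruit to Appendix Table 2.
- State in 6.9 or Section 19.0 that prohibited status governs over caution status, whether a drug is prohibited by name or by class. Say that this includes antineoplastics other than the doxorubicin given in study chemoembolization.
- Add an explicit exception, with monitoring, for fentanyl used as sedation at chemoembolization.
- Point 5.2.5 to both appendix tables, and change the first reference in the 6.9 caution paragraph from Table 2 to Appendix Table 1.

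The cost is text edits to a few sections. A few patients may need a concomitant drug changed.
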